### 3.3 Rationale

Suzhou Kintor Pharmaceutical, Inc. is developing GT0918, a new investigational androgen receptor (AR) antagonist for the treatment of castration resistant prostate cancer (CRPC) and metastatic hormone sensitive cancer (mHSPC). The anticipated dosing regimen is once daily for oral administration. The proposed dosage form for clinical research is 100 mg per tablet.

GT0918 is a new investigational second generation of androgen receptor antagonist with more specificity and activities in inhibiting androgen receptors; in particular, it can maintain a pure role of an antagonist because it does not activate AR of CRPC cells compared to bicalutamide. As compared to enzalutamide, GT0918 has improvement in target potency as well as drug disposition properties. It is expected to reduce drug accumulation, which may reduce drug exposure in the CNS, therefore avoiding the CNS side effects of enzalutamide such as seizure, thus improving the safety profile.

In addition, GT0918 demonstrates a dual mechanism of action in cell assays, i.e., highly effective in inhibiting AR as well as other pharmacological effects such as down-regulation of AR expression; a mechanism that is not seen in bicalutamide or enzalutamide. Considering that over-expression of AR is one of the major mechanisms for generating resistance in castration therapy for prostate cancer, GT0918 could alleviate resistance of castration therapy for prostate cancer as result from the dual mechanism of action thus is expected to be a more effective and less toxic second-generation CRPC drug therapy. GT0918 may provide clinical benefits to some of the subjects who have developed resistance to enzalutamide or abiraterone treatments. These properties make GT0918 an ideal candidate suitable for testing in subjects with metastatic hormonal sensitive prostate cancer (mHSPC) or metastatic castrate resistant prostate cancer (mCRPC).

In the Phase I/II study, GT0918-US-1001, part I study of dose escalation, 40 subjects have been treated with GT0918 at seven dose levels (detail see above 3.2.2), who progressed on multiple lines of therapies including abiraterone and enzalutamide. GT0918 has been generally well-tolerated. Early phase I study performed in China included 19 subjects who were treated with

Suzhou Kintor Pharmaceutical, Inc.  
Protocol#: GT0918-US-1002

Proxalutamide (GT0918)

GT0918 in various doses 50 mg, 100 mg, 200 mg, 300 mg and 400 mg over 3 months. Mild to moderated drug-related AEs were reported, such as hypercholesterolemia, hyperglycemia, hyperglyceridemia, peripheral edema, hot flush, fatigue, nausea, constipation, hepatotoxicity. Based on clinical outcomes from both phase I studies, this expanded/phase II is recommended to further evaluate the safety and tolerability of GT0918 at 2 dosages: 400 mg and 500 mg in eligible subjects with mCRPC and mHSPC.

## 4 STUDY OBJECTIVES (EXPANDED/PHASE II)

### 4.1 Primary Objective

- To evaluate the safety and tolerability of GT0918 in subjects with mHSPC or mCRPC who failed either abiraterone or enzalutamide treatment, and to determine the RP2D for Ph III and/or other confirming studies

### 4.2 Secondary Objectives

- To evaluate radiographic progression-free survival (rPFS)
- To evaluate objective response rate
- To evaluate time to radiographic progression
- To evaluate PSA 50% decline and maximum change at 12 weeks
- To evaluate PSA doubling time (PSA DT)
- To evaluate the time to PSA progression
- To identify exploratory biomarkers to characterize androgen receptor (AR) inhibition and/or down-regulation by GT0918

## 5 STUDY ENDPOINTS

### 5.1 Primary Endpoint

- To select the recommended Phase II dose (RP2D) for future clinical trials and/or other confirmatory studies based on safety, tolerability and dose exposure

## 5.2 Secondary Endpoints

- To evaluate safety and tolerability of GT0918 assessed by AEs, SAEs, vital signs, ECG, physical exam, and laboratory safety assessments of 400 mg daily vs. 500 mg daily over 6 months or longer treatment.
- To evaluate proportion of subjects with a  $\geq 50\%$  PSA suppression or increased PSA doubling time at 12 weeks and 24 weeks
- CT/MRI and bone scans will be done at 12-week intervals to determine time to progression, and percentage of radiographic disease progression at 6 and 12 months
- Exploratory markers include circulating tumor cells, cell free circulating tumor DNA (ct-DNA)/RNA (ct-RNA), etc.

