**Reference product, dosage and mode of administration**

No reference product will be used.

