## **7 SELECTION AND WITHDRAWAL OF SUBJECTS (Expanded/Phase II)**

### **7.1 Inclusion Criteria**

1. Signed informed consent obtained prior to any study-related procedure being performed.
2. Subjects at least 18 years of age or older at the time of consent.
3. Subjects with histologically confirmed mHSPC or mCRPC who received abiraterone or enzalutamide for the hormonal treatment of 6 months or longer.
4. Subjects with mHSPC are required to have no prior ADT or orchiectomy. For mCRPC, ongoing androgen deprivation therapy with a luteinizing hormone-releasing hormone (LHRH) "super-agonist" or antagonist, or bilateral orchiectomy. Serum testosterone level is < 50 ng/dL (< 0.5 ng/mL, < 1.7 nmol/L) at screening.
5. Metastatic disease documented by computed tomography (CT)/magnetic resonance imaging (MRI) or bone scan.
6. Progressive disease despite hormonal treatment with abiraterone or enzalutamide, but not both. However, if either of these 2 drugs was used less than 3 months before discontinuation due to toxicity, the subject is eligible. Progressive disease is defined by 1 or more of the following criteria:

- a. Subjects with a rising prostate specific antigen (PSA) value  $> 2$  ng/mL in at least 2 measurements, at least 1 week apart. If the confirmatory PSA value is less than the screening PSA value, then an additional test for the rising PSA is required to document progression.
- b. Subjects with measurable disease, progression defined by Response Evaluation Criteria in Solid Tumors (RECIST) 1.1 criteria
- c. Subjects with metastatic bone disease, progression defined by 2 or more new lesions in a radionuclide bone scan.

7. ECOG performance status of 0-1

8. Screening blood counts of the following:

- a. Absolute neutrophil count  $\geq 1500/\mu\text{L}$
- b. Platelets  $\geq 100,000/\mu\text{L}$
- c. Hemoglobin  $> 9 \text{ g/dL}$  (if asymptomatic).

9. Screening chemistry values of the following:

- a. Alanine aminotransferase (ALT) and aspartate transaminase (AST)  $\leq 2.5 \times$  upper limit of the normal reference range (ULN)
- b. Total bilirubin  $\leq 2 \times$  ULN
- c. Creatinine  $\leq 1.5 \times$  ULN
- d. Albumin  $> 2.8 \text{ g/dL}$ .

10. At screening, life expectancy of at least 6 months.

11. Subjects whose partners are women of childbearing potential (WOCBP) must use an adequate method of birth control while on study drug and for at least 3 months after discontinuation of study drug.

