### 9.2 Expanded/Phase II Study Visits

#### 9.2.1 Screening Visit

Screening Visit (days -21 to -1) will occur within 3 weeks prior to Day 1. Re-screening is allowed for some special cases where clinical reassessments are required and approved by medical monitor. Assessments performed as part of standard of care and obtained prior to

informed consent but within 28-days of enrollment may be used in some cases to satisfy the screening criteria. The following assessments and tests will be performed:

- Informed consent
- Inclusion/Exclusion Criteria
- Demographics, Medical and Surgical History
- Schedule CT or MRI, or/and bone scan preferably within -7 days of Day 1 of treatment

OR

Document/Assess Disease Status (Obtain CT or MRI or/and bone scan that may be performed as part of standard care within 6 weeks prior to Day 1 to confirm screening requirements)

- Vital Signs, including Height and Body Surface Area (BSA) (Screening only)
- Complete Physical Exam
- ECOG performance status
- Laboratory Tests (fasting where applicable): hematology, PT/PTT/INR, chemistry including electrolytes, urinalysis, lipid profile and blood glucose, PSA, LDH, and testosterone
- 12 lead ECG
- Assess Prior/Concomitant medication usage. If pain medications are taken, list name, dosage, frequency, etc.

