### 9.2.2 On-Treatment Visits

#### Cycle 1, Day 1 (Week 1) before dosing for ALL subjects

- Admit to Clinical Research Unit (CRU)
- Confirm screening eligibility test results are acceptable for study participation
- Review and record Interim Medical and Surgical History (prior to first dose)
- Vital signs (prior to first dose)

Suzhou Kintor Pharmaceutical, Inc.  
Protocol#: GT0918-US-1002

Proxalutamide (GT0918)

- Abbreviated Physical Exam
- ECOG (prior to first dose)
- Laboratory Tests (fasting where applicable): hematology, chemistry & electrolytes, urinalysis, lipid profile and blood glucose, PSA, and LDH
- 12 lead ECG
- Assess AEs
- Assess Concomitant Medication usage/confirmation. If pain medications are taken, list name, dosage, frequency, etc.
- Study drug disposition
- Exploratory markers: circulating tumor cells (CTC), ct-DNA and ct-RNA

#### Cycle 1 Day 15

- Subject returns to CRU
- Vital Signs
- Abbreviated Physical exam
- ECOG
- Assess for AEs
- Assess compliance by pill count
- Assess concomitant meds usage/confirmation. If pain medications are taken, list name, dosage, frequency, etc.
- Study drug disposition

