## 13 STATISTICAL ANALYSIS

A Statistical Analysis Plan (SAP) will be prepared after the protocol is approved. This document will provide further details regarding the definition of analysis variables and analysis methodology to address all study objectives. The SAP will serve as a compliment to the protocol and supersedes it in case of differences.

The statistical evaluation will be performed using the Statistical Analysis Software (SAS®) Version 9.4 or higher (SAS Institute, Cary, NC). All data will be listed, and summary tables will be provided. Summary statistics will be presented by dose group. For continuous variables, data will be summarized with the number of subjects (N), mean, standard deviation, median, minimum, and maximum by treatment group. For categorical variables, data will be tabulated with the number and percentages of subjects for each category by treatment group. No interim analyses are planned for the Phase II dose expansion study.

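### Section 5.2 counts any increase in PSA doubling time as a response, so the resulting proportion cannot be read as activity

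*Combined protocol and SAP*

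**What the plan says.** Section 5.2 lists, as a secondary endpoint, the proportion of subjects with at least 50% "PSA suppression or increased PSA doubling time at 12 weeks and 24 weeks". Sections 1 and 4.2 name PSA doubling time as an objective of its own and do not define it.

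Section 13.4 covers percentage change in PSA at Week 12, maximum percentage change, and the proportion with at least a 50% reduction at Week 12. It does not mention doubling time or Week 24. Section 13 promises an SAP: "This document will provide further details regarding the definition of analysis variables and analysis methodology to address all study objectives". No SAP text that defines doubling time is in the document supplied. Section 13 also says "Summary statistics will be presented by dose group", and no null rate or target rate is given for any PSA endpoint.

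Both arms receive GT0918, and the synopsis states "No reference product will be used".

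Pre-treatment PSA is scheduled twice:
- **Screening** (Section 9.2.1): "Screening Visit (days -21 to -1) will occur within 3 weeks prior to Day 1". Some standard-of-care assessments within 28 days of enrolment may also count.
- **Cycle 1 Day 1** (Section 9.2.2): the pre-dose laboratory list includes "urinalysis, lipid profile and blood glucose, PSA, and LDH".

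Criterion 6a in Section 7.1 asks for a rising PSA above 2 "ng/mL in at least 2 measurements, at least 1 week apart". It is one of three alternative routes to showing progression.

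**The concern.** An increase needs a comparator, and the plan names none. With no minimum increase, any slowing of PSA growth counts, including slowing that is only measurement noise. With no untreated arm, the absolute proportion shows activity only if its value under no effect is known and low. That value depends on three rules that the supplied text does not set: which pre-treatment values form the reference, how large an increase must be, and what happens when a slope is zero or negative, so that doubling time is undefined or negative.

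A reader of the study report could take a doubling-time response of 50% or 60% as evidence that the drug works in men who progressed on abiraterone or enzalutamide. If the word *or* in Section 5.2 means one combined proportion, the loose criterion could also swamp the strict one.

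**Working it through.** The plan states no figure for this endpoint, so there is none to reproduce. The check asks what the criterion would return for a drug with no effect.

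**Inputs from the protocol.** 30 subjects per arm (Section 13.1). PSA every 28 days (Table 1, Section 12.4), hence 4 values from Day 1 to Day 85 and 7 values to Day 169. Reference from screening to Cycle 1 Day 1, taken as 21 days.

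**Assumed inputs, not in the documents.** Log PSA = k·t + normal noise, with k = ln 2 / doubling time. Doubling time is lognormal with median 60, 90, 120 or 180 days and log SD 0.6. PSA CV is 5, 10 or 20%. Base case: 90 days and 10%. Each scenario used 400,000 simulated subjects.

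**Rule.** Reference slope = (log PSA at Cycle 1 Day 1 − log PSA at screening)/21. On-treatment slope = least squares through the 4 or 7 values. Doubling time counts as increased if the on-treatment slope is below the reference slope.

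**Results with no drug effect**

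| Scenario | Week 12, base | Week 24, base | Range over the input grid |
|---|---|---|---|
| 50% decline alone | 0.00 | 0.00 | at most 0.0004 |
| Constant growth, no selection | 0.50 | 0.50 | 0.50 |
| Selected on a rise; that pair is also the reference | 0.58 | 0.58 | 0.51–0.79 |
| Selected on an earlier pair 7–28 days apart, ending at screening | 0.41–0.47 | 0.40–0.47 | 0.36–0.50 |
| Growth 1.25 times faster after Day 1 | 0.38 | 0.38 | base only |
| Growth 1.5 times faster after Day 1 | 0.29 | 0.28 | base only |

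At a rate of 0.50, 15 of 30 subjects per arm would be expected to respond (95% binomial range 10 to 20).

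**Rule for falling PSA.** The reference slope is zero or negative in 14% of subjects in the base case (2–37% over the grid). If signed doubling times are compared instead of slopes, nearly all of these subjects switch to increased, because a positive doubling time exceeds a negative one: 0.50 + 0.14 = 0.64. In a separate simulation (two reference values 7 days apart, doubling time 6 months, log-PSA SD 0.2, Week 12, no selection), only the handling of falls was changed. The no-effect rate was 40% if falls count as not increased, 50% if they count as increased, 84% with signed doubling times, and 91% if falls are excluded.

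**What this does to interpretation.** Suppose 18 of 30 respond (60%, 95% CI 41–77%). The probability of 18 or more is 0.18 if the no-effect rate is 50%, and 0.997 if it is 80%.

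**If the two criteria are combined.** Combined rate = p + (1 − p)·q, where p is the 50%-decline rate and q is the doubling-time rate among the rest. Take assumed p = 0.10 and 0.30:
- **q = 0.50 in both arms:** 0.10 + 0.90 × 0.50 = 0.55 and 0.30 + 0.70 × 0.50 = 0.65. The difference falls from 20 to 10 points.
- **Other common q:** the difference is 0.20 × (1 − q), so 14 points at q = 0.30 and 8 points at q = 0.60.
- **q = 0.50 and 0.70:** 0.55 and 0.30 + 0.70 × 0.70 = 0.79. The difference is 24 points. Break-even is q = (0.75 − 0.30)/0.70 = 0.64 in the stronger arm.

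**The case against.** **The SAP may define it.** Section 13 assigns variable definitions to the SAP and lets the SAP prevail where the two differ. This stands: the supportable statement is that the supplied text does not define the criterion, not that no definition exists anywhere.

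**A definition would be enough.** Only in part. As an illustration, a four-value, 12-week pre-treatment reference with a two-fold minimum increase, falls counted as increased, still gives a no-effect rate of 0–37% at Week 12 and 0–25% at Week 24, depending on assumed growth and noise. The trial schedules only two pre-treatment values, about 3 weeks apart, or somewhat longer where the 28-day allowance is used. Older values may exist, but nothing requires their use. With only 3 weeks off the prior drug required, they could also reach back into that treatment.

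**Entry on a rising PSA.** A reader might infer that it must inflate the rate through regression to the mean. The documents do not establish the direction. At Cycle 1 Day 1 the site is to "Confirm screening eligibility test results are acceptable for study participation", so the qualifying pair may well predate the reference, and then the rate goes down. The selected rates are also limits: criteria 6b and 6c admit subjects without a rising PSA.

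**The dose comparison.** A reader might infer that the 400 versus 500 mg contrast is biased or necessarily diluted. It is not biased if one rule is applied to both randomised arms. Dilution follows only when the arms have similar doubling-time rates among the remaining subjects.

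**Combined or separate.** Sections 1 and 4.2 list the two measures separately, so *or* may mean two proportions. The doubling-time proportion has the same defect either way.

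**It is one descriptive secondary endpoint.** True, and this limits the damage.

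**Conclusion.** The point holds for this one secondary endpoint. As worded, the doubling-time criterion would be met by a large share of subjects on an inert drug in the scenarios shown: about half under constant growth and symmetric noise when slopes are compared, about 0.64 with signed doubling times, and roughly 0.3 to 0.8 across the scenarios with a screening-to-Cycle 1 Day 1 reference. The 50% decline gives about 0%. The proportion, alone or combined, therefore cannot be read as activity.

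These rates rest on assumed growth and noise, and the 0.3–0.8 span is not a bound. Acceleration was varied only in the base case. With less noise, or together with an earlier qualifying pair, it would push the rate lower. The conclusion needs none of the individual figures, only that the no-effect value is not fixed by the plan and can be high.

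A reader might go further and doubt the dose selection or the PSA results as a whole. The documents do not support that. Section 5.1 bases the recommended dose on safety, tolerability and dose exposure, and the Week 12 50% decline in Section 13.4 has its own threshold and baseline.

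**What to change.** - **Section 5.2:** do not use an increase in PSA doubling time as a responder criterion. Report the proportion with at least a 50% PSA decline by itself at Weeks 12 and 24.
- **Section 13.4:** add the Week 24 analysis. Report PSA kinetics separately and descriptively as the log-PSA slope from Cycle 1 Day 1 to Cycle 4 Day 1 and to Cycle 7 Day 1, by randomised arm, with the arm difference and its 95% CI. A slope is defined for flat and falling PSA.
- **Early leavers:** use all available PSA values up to treatment stop, and report the number of subjects contributing.
- **Change from the pre-treatment slope:** if shown, label it descriptive and state its reference period and number of values.
- **SAP:** carry the same definitions over.

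The cost is wording in Sections 5.2 and 13.4 and in the SAP, with no new samples or visits. If a combined figure was intended, the reported PSA response becomes lower. Under the base assumptions with all 30 per arm contributing, the 95% half-width for the Week 12 slope difference is 1.96 × 0.175 × √(2/30) = 0.089 log units per 28 days, against a mean slope of 0.258. Early dropout or varied treatment response would widen it.

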## 6 INVESTIGATIONAL PLANS (EXPANDED/PHASE II)

### 6.1 Description of Overall Study Design and Plan

This expanded/Phase II, open-label, randomized, and multi-center clinical study is designed to evaluate the safety, tolerability and efficacy of GT0918, an orally administered AR antagonist, in mHSPC or mCRPC subjects who failed prior treatment of either abiraterone or enzalutamide. All subjects will be randomized to either take 400 mg or 500 mg for daily administration as recommended by the phase I clinical data. Each arm will be 30 subjects. Subjects will have initial treatment up to 6 cycles with an option to continue up to additional 24 cycles as long as there is no progressive disease, no intolerable adverse event, no radiographic disease progression, no consent withdrawn by the subject or no termination of the study by the sponsor.

### 6.2 Discussion of Study Design

GT0918 is an oral androgen receptor antagonist with superior characteristics compared to currently marketed AR antagonists based on both preclinical and clinical data.

Based on clinical experience and outcomes from phase 1 (part I) dose escalation of GT0918, it is recommended for 400 mg or 500 mg oral administration daily for the first initial treatment up to 6 cycles. Dose reduction is allowed for subjects (see Section 8.6.3) who experiences any study drug related intolerable toxicities. Study drug GT0918 is suggested to be taken on an empty stomach. If dosing before meal time, it is recommended to wait 1 hour before eating. If dosing after meals, it is recommended to wait 2 hours before taking the study drug.

Suzhou Kintor Pharmaceutical, Inc.  
Protocol#: GT0918-US-1002

Proxalutamide (GT0918)

By the end of 6 cycles of initial treatment, subjects will have an end-of-6-cycles assessment to be determined for further treatment (Section 9.2.2.) Eligible subjects (without PD) have the option to be treated for additional up to 24 cycles at their assigned dose level until PD, intolerable toxicity or as investigator's discretion (Section 9.2.3). At the end of 12, 18 and 24 cycles, assessments will be performed to determine if the subjects will move into the next 6 cycle treatment.

All subjects on study drug of GT0918 are required to perform End-of-Study (EoS) assessment before termination (Section 9.2.4). A post-treatment safety window of 30 days is allowed for any possible delayed study drug-related AEs and SAEs after the last dose of study medication or end-of-study visit which ever occur later. See schedule of assessments (Appendix 1)

### **Duration of Study (expanded/phase II)**

This Phase II study is an open-label, randomized, multi-center study in mHSPC or mCRPC subjects who progressed on prior treatment with either abiraterone or enzalutamide.

The study has 2 periods, a 3-week Screening Period, a up to 6 cycles Treatment Period (+ option of continued treatment, see above). The study will be conducted at 10 centers in the United States.

## **7 SELECTION AND WITHDRAWAL OF SUBJECTS (Expanded/Phase II)**

### **7.1 Inclusion Criteria**

1. Signed informed consent obtained prior to any study-related procedure being performed.
2. Subjects at least 18 years of age or older at the time of consent.
3. Subjects with histologically confirmed mHSPC or mCRPC who received abiraterone or enzalutamide for the hormonal treatment of 6 months or longer.
4. Subjects with mHSPC are required to have no prior ADT or orchiectomy. For mCRPC, ongoing androgen deprivation therapy with a luteinizing hormone-releasing hormone (LHRH) "super-agonist" or antagonist, or bilateral orchiectomy. Serum testosterone level is < 50 ng/dL (< 0.5 ng/mL, < 1.7 nmol/L) at screening.
5. Metastatic disease documented by computed tomography (CT)/magnetic resonance imaging (MRI) or bone scan.
6. Progressive disease despite hormonal treatment with abiraterone or enzalutamide, but not both. However, if either of these 2 drugs was used less than 3 months before discontinuation due to toxicity, the subject is eligible. Progressive disease is defined by 1 or more of the following criteria:

- a. Subjects with a rising prostate specific antigen (PSA) value  $> 2$  ng/mL in at least 2 measurements, at least 1 week apart. If the confirmatory PSA value is less than the screening PSA value, then an additional test for the rising PSA is required to document progression.
- b. Subjects with measurable disease, progression defined by Response Evaluation Criteria in Solid Tumors (RECIST) 1.1 criteria
- c. Subjects with metastatic bone disease, progression defined by 2 or more new lesions in a radionuclide bone scan.

7. ECOG performance status of 0-1

8. Screening blood counts of the following:

- a. Absolute neutrophil count  $\geq 1500/\mu\text{L}$
- b. Platelets  $\geq 100,000/\mu\text{L}$
- c. Hemoglobin  $> 9 \text{ g/dL}$  (if asymptomatic).

9. Screening chemistry values of the following:

- a. Alanine aminotransferase (ALT) and aspartate transaminase (AST)  $\leq 2.5 \times$  upper limit of the normal reference range (ULN)
- b. Total bilirubin  $\leq 2 \times$  ULN
- c. Creatinine  $\leq 1.5 \times$  ULN
- d. Albumin  $> 2.8 \text{ g/dL}$ .

10. At screening, life expectancy of at least 6 months.

11. Subjects whose partners are women of childbearing potential (WOCBP) must use an adequate method of birth control while on study drug and for at least 3 months after discontinuation of study drug.

12. Subject is willing and able to comply with all protocol required visits and assessments

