**Diagnosis and Inclusion/Exclusion criteria (expanded/phase II):**

Inclusion criteria:

1. Signed informed consent obtained prior to any study-related procedure being performed.
2. Subjects at least 18 years of age or older at the time of consent.
3. Subjects with histologically confirmed mHSPC or mCRPC who received abiraterone or enzalutamide for the hormonal treatment of 6 month or longer.
4. Subjects with mHSPC are required to have no prior ADT (androgen deprivation therapy) or orchiectomy. For mCRPC, ongoing androgen deprivation therapy with a luteinizing hormone-releasing hormone (LHRH) “super-agonist” or antagonist, or bilateral orchiectomy. Serum testosterone level is < 50 ng/dL (< 0.5 ng/mL, < 1.7 nmol/L) at screening.
5. Metastatic disease documented by computed tomography (CT)/magnetic resonance imaging (MRI) or bone scan.
6. Progressive disease despite hormonal treatment with abiraterone or enzalutamide for over 6 months (but not both). However, if either abiraterone or enzalutamide were used less than 3 months before discontinuation due to toxicity, the subject is eligible. Progressive disease is defined by 1 or more of the following criteria:
  - a. Subjects with a rising prostate specific antigen (PSA) value > 2 ng/mL in at least 2 measurements, at least 1 week apart. If the confirmatory PSA value is less than the screening PSA value, then an additional test for the rising PSA is required to document progression.
  - b. Subjects with measurable disease, progression defined by Response Evaluation Criteria in Solid Tumors (RECIST) 1.1 criteria
  - c. Subjects with metastatic bone disease, progression defined by 2 or more new lesions in a radionuclide bone scan.
7. ECOG performance status of 0-1
8. Screening blood counts of the following:
  - a. Absolute neutrophil count  $\geq$  1500/ $\mu$ L
  - b. Platelets  $\geq$  100,000/ $\mu$ L
  - c. Hemoglobin > 9 g/dL (if asymptomatic).
9. Screening chemistry values of the following:

- a. Alanine aminotransferase (ALT) and aspartate transaminase (AST)  $\leq 2.5 \times$  upper limit of the normal reference range (ULN)
- b. Total bilirubin  $\leq 2 \times$  ULN
- c. Creatinine  $\leq 1.5 \times$  ULN
- d. Albumin  $> 2.8 \text{ g/dL}$ .

10. At screening, life expectancy of at least 6 months.

11. Subjects whose partners are women of childbearing potential (WOCBP) must use an adequate method of birth control while on study drug and for at least 3 months after discontinuation of study drug.

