As for the specific treatment for prostate cancer, surgical castration (radical prostatectomy, transurethral resection of prostate [TURP], and bilateral orchiectomy) and medical castration (luteinizing hormone releasing hormone [LHRH] antagonist and gonadotropin-releasing hormone [GnRH] antagonist) are the preferred means for early treatment, and they can be performed in combination with treatments such as endocrine, immune, differentiation, gene and radiation therapies. Most androgens are from the testes and a lesser amount originate from the adrenal glands; surgical castration can only remove the androgens originating from the testes, and the adrenal glands still secrete a significant amount of steroids, producing androgens and precursors of testosterone that enter prostatic tissues and are then released into the blood. Prostate cancer is highly sensitive to androgen. To achieve the purpose of treatment of prostate cancer, synthesis of androgen must be suppressed to prevent its interaction with AR on the cell surface, thereby blocking the physiological effects of androgen. The usual androgen deprivation therapy (ADT) is mainly focused on the hypothalamic-pituitary-testicular gonadal axis generated by androgen. The drug treatments are: 1) endocrine axis blocking therapy; 2) direct inhibition of androgen synthesis, and 3) androgen receptor inhibitor. For example, estrogen (Diethylstilbestrol, Transdermal estradiol and Conjugated estrogens [Premarin® tablets]) can be used to regulate the hypothalamic-pituitary-gonadal axis to reduce testosterone production; inhibitors produced by adrenal androgen (corticosteroids, ketoconazole and CYP19 inhibitor abiraterone) reduce testosterone synthesis by inhibiting the relevant enzymes. Androgen receptor (AR) antagonists in combination with anti-androgen drugs are currently the most effective drug

Suzhou Kintor Pharmaceutical, Inc.  
Protocol#: GT0918-US-1002

Proxalutamide (GT0918)

treatment to manage the prostate cancer where castration failed. Nilutamide, flutamide, bicalutamide (trade name Casodex®) and enzalutamide (trade name XTANDI®) all belong to this class of androgen receptor antagonists.

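### For mHSPC, inclusion criteria 3, 4 and 6 do not define one consistent population, so the mHSPC part of the title and primary objective lacks clear support

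*Combined protocol and SAP*

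**What the plan says.** Three inclusion criteria in Section 7.1 bear on mHSPC.

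- Criterion 3 covers both disease states: "Subjects with histologically confirmed mHSPC or mCRPC who received abiraterone or enzalutamide for the hormonal treatment of 6 months or longer".
- Criterion 6 requires progression on that drug: "Progressive disease despite hormonal treatment with abiraterone or enzalutamide, but not both".
- Criterion 4 has three parts. For mHSPC: "Subjects with mHSPC are required to have no prior ADT or orchiectomy". For mCRPC, it asks for ongoing androgen deprivation by an LHRH agonist or antagonist, or bilateral orchiectomy. A further sentence, tied to neither disease state, reads "Serum testosterone level is < 50 ng/dL" and applies at screening.

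The synopsis has the same rules. It spells out the abbreviation ("Subjects with mHSPC are required to have no prior ADT (androgen deprivation therapy) or orchiectomy") but does not say which drugs count.

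The only extended account of ADT is in Section 3.1. It says "The usual androgen deprivation therapy (ADT) is mainly focused on the hypothalamic-pituitary-testicular gonadal axis generated by androgen" and continues "The drug treatments are: 1) endocrine axis blocking therapy; 2) direct inhibition of androgen synthesis, and 3) androgen receptor inhibitor". The examples that follow put abiraterone among the synthesis inhibitors ("inhibitors produced by adrenal androgen (corticosteroids, ketoconazole and CYP19 inhibitor abiraterone) reduce testosterone synthesis") and enzalutamide among the androgen receptor antagonists.

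The title and the primary objective (Section 4.1) cover mHSPC and mCRPC. Section 3.3 ends by naming both, but Section 3.2.2 describes this study's population as mCRPC only.

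**The concern.** Every mHSPC subject must have taken a hormonal drug for six months and failed it, yet have had no prior ADT. Whether anyone can meet both rules depends on what ADT means in criterion 4, and the criteria leave that open. The testosterone sentence adds a second open question: applied to everyone, it asks men who have had neither ADT nor orchiectomy to be below 50 ng/dL.

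Two things are at stake. The first is who enters, since the ten planned centers would have to settle both questions without guidance. The second is what can be concluded. The primary objective claims safety, tolerability and a recommended dose for mHSPC as well as mCRPC. Earlier experience summarized in Section 3.2.3 is in mCRPC and breast cancer, so any mHSPC statement has to rest on the mHSPC subjects this trial enrolls.

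**Working it through.** **Planned size.** Section 13.1 gives 2 arms × 30 = 60. The synopsis gives 4 cells (dose by prior drug) × 15 = 60. The two agree. No alpha, power or effect size is stated, so there is no power calculation to repeat. Neither layout splits the 60 by disease state.

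**Who qualifies as mHSPC.** Take an mHSPC man who meets criteria 3 and 6, so prior abiraterone or enzalutamide is given. Let two facts vary: whether he ever had LHRH therapy or orchiectomy, and whether his screening testosterone is below 50 ng/dL. Apply criterion 4 under each reading of ADT and each reading of the testosterone sentence.

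| ADT in criterion 4 | Testosterone limit applies to | mHSPC men who qualify |
|---|---|---|
| Includes abiraterone and enzalutamide | everyone | none |
| Includes abiraterone and enzalutamide | mCRPC only | none |
| LHRH therapy only | everyone | no LHRH therapy or orchiectomy ever, testosterone below 50 |
| LHRH therapy only | mCRPC only | no LHRH therapy or orchiectomy ever, any testosterone |

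The four combinations give three different populations: an empty one, a residual one of never-castrated men with low testosterone, and one that admits non-castrate men.

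**Does the short-exposure exception help?** Criterion 6 admits a subject who stopped one of the drugs for toxicity within three months. Section 13.1 explains that this concerns a second drug, and that the drug progressed on is the one counted. Criterion 3 still asks for six months, so the exception does not alter the table.

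**Could the analysis separate the groups afterwards?**

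- Randomization is stratified by prior drug only (Section 13.1).
- The baseline list in Section 13.3 has no mHSPC/mCRPC variable, even under its heading on clinical state of disease.
- Safety is summarized by dose level and over all subjects (Section 13.6).

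An empty or mixed mHSPC group would therefore not show in the specified tables.

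**Possible size.** The mHSPC share is not stated. Purely as assumptions, shares of 0, 10, 25 and 50% of 60 would give 0, 6, 15 and 30 subjects, or 0, 3, 7.5 and 15 per arm on average.

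**The case against.** The strongest reply is that ADT in criterion 4 means LHRH therapy, and that criteria 3, 4 and 6 then do not conflict. Several points favor this:

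- Criterion 4's own mCRPC sentence describes ADT as LHRH therapy and sets it beside orchiectomy. The mHSPC sentence uses the same pairing.
- Criteria 3 and 6, and the baseline list in Section 13.3, call abiraterone and enzalutamide hormonal treatment, which is a different term.
- Section 8.6.1 requires LHRH therapy to continue only for subjects already on it. That is consistent with some subjects being on neither LHRH therapy nor orchiectomy.
- Section 3.1 is background, not a definition. Its list can be read as drug treatments for prostate cancer in general, and it places receptor antagonists after castration has failed.
- The testosterone sentence directly follows the mCRPC sentence and may be meant only for mCRPC.

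All of this stands as support for the narrow reading. A reader might infer from Section 3.1 that the protocol itself classes both drugs as ADT, so that eligible mHSPC is zero and half of the trial is empty. The documents do not support that. Zero follows only from the broad reading, and half could mean only one of two named disease states, not 30 of 60 subjects. Nor does anything show that sites have in fact read the criteria differently.

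The reply does not remove the problem. On the narrow reading with the limit applied to all, never-castrated men must still meet the testosterone limit. With the limit confined to mCRPC, the criteria are consistent, but non-castrate men are pooled with castrate men and nothing planned tells them apart.

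**Conclusion.** The concern holds as a defect of definition and scope. Each reading of the criteria leaves the mHSPC claim without clear support: no eligible subjects, a residual group that must meet the testosterone limit without castration, or a group merged into mCRPC in every planned summary.

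The size cannot be given as a number of subjects, because no mHSPC target or split is stated. The planned total of 60 and the dose-by-prior-drug layout are unaffected.

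The conclusion rests on the text of the current protocol. Section 13 announces a separate SAP that takes precedence over the protocol, and none is included in the document reviewed. It could add summaries by disease state, but these would not settle who was eligible. The stronger statement, that no mHSPC subject can enter, should not be made.

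**What to change.** 1. In Section 7.1 and the synopsis, write criteria 3, 4 and 6 separately for mHSPC and mCRPC. State what counts as prior ADT for mHSPC and to whom the testosterone limit applies. Which rule is right is for the sponsor and its clinical advisers to decide.
2. Bring Section 3.1 (the account of ADT) and Section 3.2.2 (population given as mCRPC only) into line with the revised criteria and the title.
3. Add disease state to the baseline list in Section 13.3 and report the number of mHSPC subjects by arm, so that a reader can see what any mHSPC statement rests on.
4. If no consistent mHSPC group remains, or none was enrolled, limit the title, primary objective and recommended-dose conclusion to mCRPC.

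First enrollment is given as 2Q2019 and this version is dated 18 March 2021. If eligibility can no longer be changed, items 3 and 4 still apply at reporting. The cost is amendment wording, one baseline variable and possibly a narrower stated scope. No change to the sample size is needed.
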